The inclusion questionnaire/interview will select the average healthy adult population for analysis of the clearance rate of blueberry components (phytonutrients) through the body over time. Thus, the study will include male and female adults between 25-65 years because there is evidence that adolescence and the elderly have different metabolic processes (particularly differing absorption and metabolism) compared to this age range; non-smokers, non-tobacco users [no vaping or dipping (tobacco chewing)], or who ceased it \geq 6 months ago because it is known to affect metabolic processes; who present no allergies to fruits or vegetables containing polyphenolic (e.g. anthocyanins, flavonoids) and phenolic acids such as blueberries, red apple, strawberry, red orange, purple onion and broccoli because participants will be served blueberries; who present no allergies to whey protein or salicylates because participants will be served with blueberries, which contain traces of salicylates, and the blueberry-rich protein bar containing whey protein; who are generally healthy and without chronic diseases including cancer, type 1 and 2 diabetes; who are not prescribed thyroid or hypoglycemic medication or hormone replacement therapy (HRT) (due to the likely concomitant effects that these medications cause on the primary endpoint in the trial), otherwise, it can impact physiological processes associated with digestion and absorption; who has not been consuming any phytonutrient-containing supplements (e.g. with berry, cocoa, coffee or tea extracts) for at least a month before the study and willing to not consume it during the study, otherwise, it would interfere with the analysis of the phytonutrients after consumption of the treatments for this study; who lives within 40 miles from the NCRC campus to avoid drop-outs due to traffic and the required early morning visits; those agreeing to restrict dietary intake of rich sources of phytonutrients targeted on the study (Annex 9) during the wash-out and clinical sampling periods, agreeing to comply with study procedures involving the collection of urine and blood samples, and to record their additional dietary intake over 2 days before each feeding visit, and two days after the intake of the blueberries or blueberry product, otherwise, this study would not be suitable for them. The clinical screening will enroll/include those who have BMI ≥ 18.5 and ≥ 30 (lbs/in² x 703) and a successful (i.e., within normal range for healthy individuals) biochemical, hematological and urine analyses assessed by the clinical advisor, as the design of the study is to establish bioequivalence in healthy middle aged humans and unhealthy, or adolescence or the elderly have altered absorption and metabolism. Studying these groups would require considerably higher participant numbers, which will be the focus of future investigations.

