
Medical diets to control for metabolic disorders, including obesity are an exclusion criteria of the present study as it will negatively impact our primarily study focus; however healthy individuals on vegetarian or vegan diets will not be excluded and we will make concessions for their meal choices during the study days.

Here we define a supplement or health supplement refers to any dietary ingredient which is consumed in a format which is extracted from a food or plant. For example, vitamins, minerals, amino acids, herbs or botanicals, or even components or extracts from plants or animals such as extracts from fruits or omega-3-fatty acids from fish are generally considered supplements. These are most often consumed as a powder, pill or beverage, like an energy shot or drink. You may consume vitamins or minerals or amino acids or protein drinks or bars consumed as a meal replacement as long as it is typical to your usual diet and you consume this regularly.

In the case where these are consumed accidentally, participants are asked to simply write this in their food intake diary and try to avoid it in the future, or if its within one week of the study visit, to repeat it on subsequent visits for consistency.

Is there any relationship between researcher and participants - such as teacher/student; employer/employee?

No

What is the justification for using this participant group instead of an unrelated participant group? Please outline the steps taken to mitigate risks to participants from the pre-existing relationship, including power dynamics of this relationship and/or perceived coercion.

Describe any risks associated with conducting your research with a related participant group.

Describe how this relationship will be managed to reduce risk during the research.

How will risks to confidentiality be managed?

Address any concerns regarding data quality (e.g. non-candid responses) that could result from this relationship.

In the following questions describe in lay terms all study procedures that will be experienced by each group of participants in this study. For each group of participants in your study, provide a step-by-step description of what they will experience from beginning to end of the study activities. Should you prefer, you can upload a detailed study procedure packet and refer us to that document in this text box. If you choose to upload a procedures packet, do not discuss procedures in the below text box.

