2. After eligibility is confirmed through phone or email inclusion questionnaire (Annex 2A or 2B), the potential participants will receive a package providing complete description of the study and consent procedures (Annex 3) via email or mail. If still willing to participate, they will be scheduled for a consent visit at the Plants for Human Health Institute (PHHI; North Carolina Research Campus, [name]), when they will be provided a brief presentation of the study and volunteers will be encouraged to ask questions. A reminder will be sent 48h before this visit. It will be explained that volunteers will be given a list of foodstuffs to “avoid” and “limit”, and alternatives to them, during the wash-out week and visit days (Annex 9); the intake of tea and coffee (as major providers of berry phytonutrients in the US diet) will be limited to a combined intake of 2 medium cups (12-16 oz) per day during washout, but none on the day before the feeding visit and on study visit days 1 and 2, and the intake of alcohol will also be regulated based on the recommendations of the Food and Drug Administration. Adherence to the low-berry-phytonutrient diet will be assessed using the food intake record (Annex 10), which the participants will be asked to provide during the two days preceding each feeding visit day, and the day of the feeding visit and following day. Participants will also be required to refrain from taking phytonutrient-containing supplements (e.g. with cocoa or coffee or berry extracts) for at least 1 month prior to the assessment visits, and throughout the trial. Volunteers will be advised to maintain their habitual lifestyle during the study (e.g. dietary intake, exercise levels and non-smoking habits). It is especially important that participants do not experience substantial shifts in body weight/body composition during the study, as fluctuations are likely to affect the endpoints in the study (i.e. phytonutrient metabolism). If still interested in participating in the study, they will be asked to sign the study consent form (Annex 5). After signing the consent form, inclusion/exclusion of participants will be verified via confirmation of their BMI, and via a medical history and medication use questionnaire (Annex 16). During this visit, participants will manifest availability for scheduling a clinical screen after a cooling-off period of a minimum of 24 hours. The clinical screening at the Clinical Services Facility at the Nutrition Research Institute-Human Research Core will be scheduled via email or phone (Annex 7A), and a reminder about it will be sent 48h before this visit (Annex 7B). Participants will be advised to follow 10-hour fasting (except for water) and to arrive hydrated at the clinical screening visit. Any sample will be collected only after the consent form is signed by the volunteer.

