5. The participants will have at least one week of washout before starting each of the four feeding visits, when they will consume a diet low in berry phytonutrients as directed by the dietary exclusion list (Annex 9). Participants will be reminded (either via mail or email; Annex 12) about the starting day of the dietary washout procedure 48h prior to it. They will be scheduled (either via mail or email; Annex 12) to pick up two 24h-urine collection kits with further instructions for use (Annex 13). Participants will be provided with standardized blueberry-phytonutrient-free meals and beverages during the treatment visit days 1 and 2 of each feeding visit. The arrangement of meals, blueberries, protein bar and macronutrient-matched beverages to be served to participants will occur in the Metabolic Research Kitchen at the UNC-CH Nutrition Research Institute, established on the NCRC campus. The standardization of the pre-feeding visit meals (two days prior to feeding visit) across the four pre-blueberry product feeding periods is necessary to control for any effect of recent background dietary intake on repeat biological assessments. Five days before the feeding visit day participants will be reminded (either via mail or email; Annex 14) to pick up two 24h-urine collection kits and be provided with further instructions for use (Annex 13), which will coincide with the last 48h of the washout. Three days prior to the feeding visit, at the time of urine collection kit pick up, participants will be reminded to fill out the two-day food intake record, and to come fasted for the visit day at the Clinical Services Facility at the Nutrition Research Institute-Human Research Core. A reminder about each feeding visit day will be sent via email or phone call 24h prior to that (Annex 15).

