6. The visit days will occur during weekdays. In the first feeding visit day, volunteers will arrive at the research facility in a fasted state (having consumed only water for the preceding 10 hours), the clinical team will take receipt of previously collected biological samples (-48h and -24h urine collections) and the study coordinator will check the food intake record from the two preceding days. Also, a researcher or suitably qualified phlebotomist will complete a basic medications assessment/questionnaire (Annex 16A) to establish fitness to proceed (e.g. to assess if the participant has fasted correctly, is free from symptoms indicative of compromised health), and record any medications being used onto the medical questionnaire. Modification to these medications (e.g. dose changes) during the study must be reported, and

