amended to this original record. The participant's resting blood pressure, height, and weight will be measured by the study coordinator, research technician or a suitably qualified phlebotomist. Additionally, urine (0-9h, 9-24h and 24-48h) and blood samples (at 0, 1, 3, 6, 9, 24 and 48 h) will be collected to assess aspects of absorption, distribution, metabolism and excretion (ADME) of berry phytonutrients. On visit day 1 of every study period, participants will have the option to have their blood drawn via single needlestick or cannula. For either option, the phlebotomist will make two attempts per vein and, if unsuccessful, a second qualified person may attempt one time. If the participant opts for cannula placement, he/she will be instructed not to bend the arm in which the cannula is inserted. They are not to leave the building with the cannula in place and are to come back to the lab area every hour to have the cannula flushed with saline. Even though the cannula is flushed with saline between successive blood draws, there is a possibility it could become blocked in which case remaining samples would be collected via single needlestick venipuncture, with the consent of the participant. Otherwise, the participant who chooses to have blood drawn via a cannula and who is comfortable with it will have it up to the last blood draw on visit day 1, which is for up to 9.5 hours. The participant will be instructed not to access the cannula at any time. Access to the cannula should be by study staff only. Those failing to comply with fasting or dietary restrictions at first visit will require a further one week washout period; repeated failure to follow the fasting or dietary guidance during the study may result in withdrawal from the trial (Annex 17) and compensation (when applicable) for their inconvenience of potentially taking some time off from work for the study, disrupting their lifestyle via restricted consumption of certain foods during the study, and for any undertaken feeding visits (Annex 8) will be provided. This procedure will be repeated across 3 other visits. In the first feeding visit, the participant will receive either, in randomized order, one serving (approximately 5.3 oz) of a standard commercially available blueberry variety (i.e., cultivar), one serving of the blueberry variety screened for either having a high or low phytochemical content, a protein bar enriched with the equivalent of one serving of blueberries or a macronutrient-matched control beverage. After the blueberries, the protein bar or the control beverage is given on day 1 of each feeding visit, breakfast will be provided, as well as lunch, dinner and snacks. All food will be purchased pre-packaged at a local grocery store, including Foodlion LLC, stored within their expiration date at the UNC Metabolic Kitchen. Any food that requires preparation for single serving such as breakfast will be handled by personnel certified with ServSafe® Food Handler certification. Food that needs to be taken home by participants will be pre-packaged, commercially available and transported in a cooler for safe handling. Blood pressure, height, and weight measurements, and potential medication and physical activity change record will be done on days 2 and 3 of each feeding visit. Participants will be asked to record their food and beverage intake during visit days 1 and 2, and to repeat these intakes on the following three feeding visits.

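### The protocol tells participants to repeat an accidental supplement before later visits, with no exception for products containing the phytonutrients being measured

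*Protocol*

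**What the plan says.** The supplement paragraph at the end of the Protocol's inclusion and exclusion criteria defines supplements broadly, including "herbs or botanicals, or even components or extracts from plants or animals such as extracts from fruits". After accidental use, the participant is to record it in the food diary and try to avoid it in future or, "if its within one week of the study visit, to repeat it on subsequent visits for consistency".

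Other parts of the Protocol bear on the same event:

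- **Inclusion criteria:** phytonutrient-containing supplements are barred before and during the study, "otherwise, it would interfere with the analysis of the phytonutrients after consumption of the treatments for this study".
- **Procedures item 2:** participants must abstain from them "for at least 1 month prior to the assessment visits, and throughout the trial".
- **Procedures item 5:** "The participants will have at least one week of washout before starting each of the four feeding visits". Pre-visit meals are standardised because this is "necessary to control for any effect of recent background dietary intake on repeat biological assessments".
- **Procedures item 6:** on visit day, "the study coordinator will check the food intake record from the two preceding days". For lapses, "Those failing to comply with fasting or dietary restrictions at first visit will require a further one week washout period", and repeated failure may lead to withdrawal.

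The SAP does not say how a period affected by supplement intake is to be handled.

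**The concern.** The trial compares blueberry-derived metabolites across four products within each participant. A berry, cocoa, coffee or tea extract supplies compounds of the kind being measured. For such a product the repeat rule asks for intake that item 2 forbids and that the inclusion criteria describe as interference. It also undercuts the low-phytonutrient week before each visit. A participant cannot follow both instructions.

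What is at stake is the cleanliness of the affected participant's data. One accident contaminates one period. The rule then contaminates every later period on purpose, and few or no clean periods remain for a sensitivity analysis.

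**Working it through.** **Inputs.** There are four feeding visits (Protocol, procedures item 5), and item 6 counts three visits after the first. Treatment order is randomised. The number of completers is 24 (Protocol, participant numbers). The documents give neither the frequency of accidental use nor the dose.

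**Counts per affected participant.** Let the accident precede visit v. Four periods give C(4,2) = 6 pairwise treatment contrasts.

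- Periods exposed under the repeat rule: 5 − v.
- Deliberate re-exposures: 4 − v. At v = 1 this is 3, matching the protocol's count of later visits.
- Contrasts with unequal background (one period exposed, one not): (5 − v)(v − 1).
- Contrasts between two unexposed periods: C(v − 1, 2).

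| Accident before visit | 1 | 2 | 3 | 4 |
|---|---|---|---|---|
| Periods exposed, repeat rule | 4 | 3 | 2 | 1 |
| Deliberate re-exposures | 3 | 2 | 1 | 0 |
| Unequal contrasts, repeat rule | 0 | 3 | 4 | 3 |
| Unexposed contrasts, repeat rule | 0 | 0 | 1 | 3 |
| Unequal / unexposed, record only | 3 / 3 | 3 / 3 | 3 / 3 | 3 / 3 |
| Unequal / unexposed, re-washout | 0 / 6 | 0 / 6 | 0 / 6 | 0 / 6 |

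The re-washout row assumes that the lapse is detected and that the rescheduled visit is clean. If the four timings are equally likely (an assumption), the means for repeat, record only and re-washout are 2.5, 3.0 and 0 unequal contrasts, and 1.0, 3.0 and 6.0 unexposed contrasts.

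**Effect on a mean contrast.** Let b be supplement-derived AUC as a fraction of product AUC, and k the number of affected completers. I assume b = 0.05 to 0.5 and k = 1 to 3. With all 24 orders equally likely and accidents unrelated to the assigned product:

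- The probability that a given contrast is unequal is p = unequal contrasts / 6 = 0, 1/2, 2/3, 1/2 for v = 1, 2, 3, 4.
- The background difference is +b or −b, each with probability p/2, and otherwise 0. Its mean is 0 and its SD is b√p = 0, 0.71b, 0.82b, 0.71b.
- The SD of the shift in the mean contrast is b√(kp)/24. The low end is 0.05 × √0.5 / 24 = 0.0015. The high end is 0.5 × √(3 × 2/3) / 24 = 0.029. For accidents before visits 2 to 4 this is 0.15% to 2.9% of product AUC.
- If every affected participant happened to be aligned in one direction, the bound would be kb/24: 0.05/24 = 0.2% up to 1.5/24 = 6.3%.

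**The case against.** **Constant background is a legitimate aim.** This is the strongest defence. If the accident precedes visit 1 and is repeated three times, a constant additive background cancels in all six contrasts, so scoring that case as 0 of 6 unexposed looks harsh. Averaged over timings, the repeat rule also gives slightly fewer unequal contrasts than simply recording the intake (2.5 against 3.0). This stands: on unequal background alone, repeating is worse than recording only before visit 3. Cancellation needs all four periods exposed, however, and it does not restore the reported concentrations, which stay raised in every period including control. The relevant comparator is re-washout, which the protocol already uses for other lapses.

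**The wording could be narrower.** The sentence just before the instruction concerns vitamins, minerals, amino acids and protein products, and the rule might refer only to those. Since they are allowed when habitual, an instruction about accidental use that should be avoided fits the full definition better. The narrow reading cannot be excluded, and it would need the same clarification.

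**The lapse rule may not apply.** A reader might infer a flat contradiction with item 6, or that a participant who obeys the repeat rule risks withdrawal. The documents do not support going that far. Item 6 names fasting and dietary restrictions at the first visit, not supplements. Its later statement that the procedure is repeated at the other three visits does not make clear what it covers. The repeat rule sits badly with item 6, but the firm conflict is with item 2 and the inclusion criteria.

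**The effect may be negligible.** Item 2 allows two cups of tea or coffee a day until two days before the visit, so intake early in the week may lie at the low end of b. The −48 h and −24 h urine and 0 h blood could also reveal raised background. Both points stand, though neither document says what follows from a raised value.

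**Re-washout is not perfect.** The record checked on visit day covers two days, so earlier intake depends on self-report.

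**Conclusion.** The point holds for phytonutrient-containing products on the most natural reading of the supplement paragraph. The repeat instruction conflicts directly with the trial-long ban and with the protocol's own reason for it, and it weakens the washout. It deliberately re-exposes 3, 2, 1 or 0 later visits and equalises background across all four periods only for an accident before visit 1.

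A reader might infer that the rule biases the treatment comparison. The documents do not support that: with randomised order and accidents unrelated to the product, the expected shift is zero. The harm is noise, raised absolute levels and lost clean periods. The range of 0.15% to 2.9% rests wholly on the assumed b and k. The effect is probably small, and the correction is worth making because it is cheap. For non-phytonutrient products the rule is reasonable as it stands.

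**What to change.** 1. In the supplement paragraph, limit the repeat instruction to products without phytonutrients.
2. For phytonutrient-containing supplements, state that intake detected within the washout week leads to a further one-week washout and rescheduling at any of the four visits, and is recorded as a deviation. Deliberate re-exposures then fall from 3, 2, 1, 0 to 0.
3. In the SAP, flag any affected period that was not rescheduled and rerun the treatment contrasts with that period set to missing.
4. Optionally, ask on visit day about supplements taken in the previous seven days. The visit questionnaire (Annex 16A) is not among the documents and may already do so.

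**Cost.** One wording amendment to the IRB and one dataset flag. Each rescheduled visit costs a one-week delay, a lost clinic slot, and repeats of the two 24 h urine collections and the food record. At the Protocol's compensation rates that is up to 2 × $5 + $4 = $14 if repeats are paid, plus travel of up to 40 miles × $0.58 = $23.20 where claimed. Detection still depends on self-report.

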
The participants will be asked to choose their standardized low-berry-phytonutrient meals from a list of foods provided (breakfast, lunch, dinner and snacks) based on the following foods: white bread*/ bagel*/white roll* with cheese, cream cheese, honey, butter, salad dressing, ham, turkey, chicken, and or roast beef, chickpeas, plain breakfast biscuit, hard boiled eggs, chips, white rice, macaroni and cheese, noodles, cucumber, baby carrots, peas, canned or dried pineapple, canned or dried peaches, crackers (no wholemeal, dark chocolate, red fruits), butter cookies; and beverages: water (mineral, flavored or sparkling), milk (1% or 2% reduced fat, skim, lactose-free, or rice milk), diet soda, artificial fruit drink. During their full day visit to the clinic and the following morning, they will be asked to abstain from consuming coffee or tea which may result in the development of a headache which can be caused from caffeine withdrawal. Caffeinated diet beverages will be provided should participants wish to consume them as an alternative to coffee or tea.

*Available as plain or gluten-free

7. Between the feeding visits, subjects will receive a "thank you" email about their participation and a reminder that they can observe approximately 2 weeks (11 to 20 days depending on scheduling constraints) of free-living compliance break (Annex 18), allowing them to return to their normal dietary habits and take a break from the study regime. This will be followed again by seven days of wash-out, urine collection (one collection at -48h and another collection at -24h) and recording of their food intake for two days before the next feeding visit day. This will be repeated for the remaining three feeding visits, including the reminder emails or phone calls previously mentioned.

8. The circumstances by which researchers may initiate participant withdrawal from the trial will be stated at each visit, as well as the need for participants to inform the research team regarding adverse events and serious adverse events during the study. At the end of the approximate 3-month trial, an exit questionnaire will be completed by the participant (Annex 19), which will give an opportunity to capture information regarding the participant experience and including

questions related to adequate blinding during the two berry treatments. In addition, participants will receive an email about their contribution to the study, which will be conducted following Good Clinical Practice.

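### The coffee and tea ban does not name day 3, when the 48 h blood draw is taken and the last urine interval ends

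*Protocol*

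**What the plan says.** The protocol states the coffee and tea rule twice.

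- **Study procedures, step 2.** It singles out "the intake of tea and coffee (as major providers of berry phytonutrients in the US diet"). A cap of two medium cups a day is tied to the washout. Around dosing the rule is stricter: "but none on the day before the feeding visit and on study visit days 1 and 2".
- **Meal-choice paragraph after step 6.** "During their full day visit to the clinic and the following morning, they will be asked to abstain from consuming coffee or tea". The sentence goes on to warn of caffeine-withdrawal headache.

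Sampling continues to day 3. Step 6 schedules blood to 48 h and a urine interval of 24-48 h. It also treats day 3 as part of the visit: blood pressure, weight and medication checks "will be done on days 2 and 3 of each feeding visit".

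There are also general dietary restrictions.

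- Step 2 gives participants a list of foods to avoid and to limit, "and alternatives to them, during the wash-out week and visit days (Annex 9").
- The inclusion criteria require them to "restrict dietary intake of rich sources of phytonutrients targeted on the study (Annex 9) during the wash-out and clinical sampling periods".
- The recruitment section repeats this for the clinical visit periods.
- The exclusion criteria remove anyone not prepared to keep the restrictions in the preceding week and during each feeding visit.

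**The concern.** A participant who follows the day-specific rule to the letter could have coffee or tea on the morning of day 3, shortly before the last blood sample and while the last urine interval is still open. The protocol itself names these drinks as important sources of the compounds under study, and its stated aim is clearance over 48 h (step 4). SAP section 1.2 derives half-life, AUC, AUMC, clearance and mean residence time from these samples.

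The last sample has most influence on the terminal slope. A drink taken before the draw in one period but not in another would add noise to within-participant comparisons, and these are the purpose of the crossover. Later analysis could not remove that noise, especially if the drink was not recorded.

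**Working it through.** **1. Do other stated controls cover day 3?**

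| Control | Where stated | Days covered |
|---|---|---|
| Coffee and tea ban (fuller form) | Step 2 | Day before dosing, days 1 and 2 |
| Coffee and tea ban (shorter form) | Meal-choice paragraph | Day 1, morning of day 2 |
| Two-cup limit | Step 2 | Washout |
| 10 h fast, water only | Step 6: "In the first feeding visit day, volunteers will arrive at the research facility in a fasted state" | Arrival on day 1 |
| Supplied meals and beverages | Step 5 | Days 1 and 2 |
| Record intake and repeat it in later periods | Step 6 | Days 1 and 2 |
| Food record | Step 2 | Two days before dosing, days 1 and 2 |
| Food record | Inclusion criteria | Two days before and two days after intake; could be read as reaching 48 h |
| Annex 9 restrictions | Step 2, inclusion criteria | Visit days and sampling periods, so probably day 3 |

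Only the Annex 9 restrictions, and one reading of the food-record wording, reach day 3. The compensation section pays for a four-day food report, which fits two days before dosing plus days 1 and 2.

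**2. Length of the gap.** The documents give no dosing time, so I assume 07:00-09:00. The step 2 ban then ends at midnight after day 2, and the 48 h draw falls at 07:00-09:00 on day 3. That leaves 7-9 h uncovered, or 7/24 to 9/24 = 29-38% of the last urine interval. Most of it is overnight, so what remains in practice is a morning drink.

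**3. AUC0-48.** The SAP leaves the PK model open, so I assume the linear trapezoid rule. At 0, 1, 3, 6, 9, 24 and 48 h the weights are 0.5, 1.5, 2.5, 3, 9, 19.5 and 12 h, which sum to 48. The 48 h sample has 12/48 = 25% of the time weight.

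Its share of the AUC itself is smaller. Assume mono-exponential decline from time 0 with starting value 1:

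- Half-life 12 h: the 48 h value is 0.0625 and the weighted sum is 17.12, so the share is 12 × 0.0625 / 17.12 = 4.4%.
- Half-life 24 h: the 48 h value is 0.25 and the weighted sum is 26.46, so the share is 12 × 0.25 / 26.46 = 11.3%.

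A 10% rise in the 48 h value therefore moves AUC0-48 by about 0.4% or 1.1%.

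**4. Treatment contrast.** SAP section 2.3 interprets the treatment effect as an additive difference in AUC. With background b at 48 h in both periods, (AUC_T + 12b) − (AUC_C + 12b) = AUC_T − AUC_C. With unequal background the shift is 12(b_T − b_C), so a difference of 1 concentration unit moves that participant's contrast by 12 unit-hours.

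**5. Terminal half-life.** Assume a log-linear fit to 9, 24 and 48 h. The mean time is 27 h, the deviations are −18, −3 and 21, and the sum of squares is 324 + 9 + 441 = 774.

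- Leverage of the 48 h point: 1/3 + 441/774 = 0.903.
- Its weight in the slope: 21/774 = 0.02713 per h.
- Effect of a 10% rise at 48 h: the rate constant falls by 0.02713 × ln(1.1) = 0.00259 per h.
- Half-life 12 h: ln 2 / (0.05776 − 0.00259) = 12.6 h.
- Half-life 24 h: ln 2 / (0.02888 − 0.00259) = 26.4 h.

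The 10% is illustrative. The documents do not show how often participants would drink coffee or tea on day 3, or how far it would raise the 48 h value.

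**The case against.** The strongest reply is that day 3 is already restricted. The recruitment section, the inclusion criteria, the exclusion criteria and step 2 all extend the diet to the visit or sampling period, and step 6 allows withdrawal for repeated breaches. The operative list is Annex 9, and neither it nor the other participant materials can be seen. Much of this stands: day 3 probably does fall within the restricted period. However, Annex 9 holds both an avoid list and a limit list, and the visible text does not say which applies to coffee and tea on day 3. A participant given a rule by named day can reasonably take an unnamed day as exempt.

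The second reply is that the effect is small and not directional. This also stands. Treatment order is randomised and no stated reason links day 3 drinking to treatment.

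A reader might make three stronger inferences that the documents do not support:

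- **Day 2 is open from midday.** The shorter sentence read alone suggests this. Step 2 bans coffee and tea on all of day 2, and following step 2 satisfies both statements.
- **A quarter of AUC0-48 is at risk.** The 25% is a time weight, not a share of the area.
- **The treatment comparison is biased.** Equal background cancels in the additive contrast, and unequal intake has no stated reason to follow treatment.

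**Conclusion.** The point holds as a minor one. The day-specific ban stops before the last blood sample and before the last urine interval closes. The stated fast, supplied beverages and repeat-intake rule do not cover day 3 either. The general Annex 9 restriction probably does, but the text leaves it unclear whether coffee and tea are then banned or only limited.

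The consequence is avoidable within-participant noise, mainly in terminal half-life and less in AUC, from which SAP sections 1.2 and 1.4 take the bioavailability comparison of primary interest. Its total size cannot be derived from the documents. The sensitivities above rest on assumed dosing at 07:00-09:00, the linear trapezoid rule, mono-exponential decline with half-lives of 12-24 h, and a three-point terminal fit. For metabolites that appear late, the 48 h sample would supply more of the AUC than 4-11%.

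**What to change.** State one rule in step 2, in the meal-choice paragraph and in the participant material: no coffee or tea from the day before dosing until the 48 h blood has been drawn and the 24-48 h urine collection is complete. If Annex 9 already says this, repeat it in both places.

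Extend the food record to the 48 h draw, and align the inclusion criteria, step 2 and step 6, so that any breach can be seen.

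The cost is wording, one more early morning without coffee or tea in each period, and a slightly longer food record. The caffeinated diet drinks that the protocol already offers could be made available until the draw. No extra visits or samples are needed.
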